2.1 Primary objective

[figure not shown]
To demonstrate that the efficacy of secukinumab 150 mg s.c. at Week 16 is superior to placebo in subjects with active AS based on the proportion of subjects achieving an ASAS20 (Assessment of SpondyloArthritis International Society criteria) response.

2.2 Secondary objectives

1. To demonstrate that the efficacy of secukinumab 150 mg s.c. at Week 16 is superior to placebo based on the proportion of subjects achieving an ASAS40 response
2. To demonstrate that the efficacy of secukinumab 150 mg s.c. at Week 16 is superior to placebo based on the change from baseline of high sensitivity C-Reactive Protein (hsCRP)
3. To demonstrate that the efficacy of secukinumab 150 mg s.c. at Week 16 is superior to placebo based on the proportion of subjects meeting the ASAS 5/6 response criteria
4. To demonstrate that the efficacy of secukinumab 150 mg s.c. at Week 16 is superior to placebo based on the change from baseline in total Bath Ankylosing Spondylitis Disease Activity Index (BASDAI)

5. To demonstrate that the efficacy of secukinumab 150 mg s.c. at Week 16 is superior to placebo based on the change from baseline in Short Form 36 physical component score (SF-36 PCS)
6. To demonstrate that the efficacy of secukinumab 150 mg s.c. at Week 16 is superior to placebo based on the change from baseline in Ankylosing Spondylitis Quality of Life score (ASQoL)
7. To demonstrate that the efficacy of secukinumab 150 mg s.c. at Week 16 is superior to placebo based on the proportion of subjects achieving an ASAS partial remission
8. Overall safety and tolerability of secukinumab compared to placebo as assessed by vital signs, clinical laboratory values and adverse event monitoring

3 Investigational plan

3.1 Study design

This multicenter study uses a randomized, double-blind, placebo-controlled, parallel-group design. A screening (SCR) period running up to 10 weeks before randomization will be used to assess eligibility, followed by 52 weeks of treatment.

[figure not shown]
At baseline, patients will be randomized to one of the two treatment groups:

- **Group 1: 300 patients**, secukinumab 150 mg (1 mL, 150 mg/mL) s.c. PFS at BSL, Weeks 1, 2, and 3, followed by administration every four weeks starting at Week 4
- **Group 2: 150 patients**, placebo (1 mL) s.c. PFS at BSL, Weeks 1, 2, 3, 4, 8, and 12, followed by secukinumab 150 mg (1 mL, 150 mg/mL) administration every four weeks starting at Week 16

The patients will be stratified at randomization according to the region (China and non-China). Approximately 80% of randomized patients will be from China (360 Chinese patients) in order to evaluate the efficacy and safety in this patient population. No more than 30% TNF α Inhibitor Incomplete Responders (TNF-IR) patients will be enrolled in the study.

Starting at Week 16, all patients will switch to open-label secukinumab 150 mg, including all placebo patients; however, all patients and investigators/site staff will remain blinded to the original randomized treatment group assignment (150 mg vs placebo). Study treatment will continue up to Week 48.

An end of treatment visit is to be done 4 weeks after last study treatment administration and a post treatment follow-up visit is to be done 12 weeks after last study treatment administration for all subjects (regardless of whether they complete the entire study as planned or discontinue prematurely).

Figure 3-1 **Study design**

Subjects will be instructed in detail how to self-administer the s.c. injection using PFS. Each injection will be administered into an appropriate injection site of the body (thighs, arms, or abdomen). All injections will be performed at the study site. Site personnel may administer the injections to subjects who are not able to, or feel insecure to self-administer (see [Section 5.5.4](#) for more details).

Rescue medication is not allowed until Week 20 (see [Section 5.5.6](#) for more details). However, subjects who are deemed by the investigator not to be benefiting from the study treatment based on safety and efficacy assessments or for any reason of their own accord will be free to discontinue participation in the study at any time.

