Enrollment	Point/ time of patient entry into the study; the point at which informed consent must be obtained (i.e., prior to starting any of the procedures described in the protocol)
Epoch / Period	A portion of the study which serves a specific purpose. Typical Epochs are: screening/recruitment, wash-out, treatment, and follow-up
Escape medication	Any new therapeutic intervention or a significant change to ongoing therapy made because a subject is experiencing either no benefit from participation in the trial or worsening/ exacerbation of their disease
Inadequate response to TNF α	Active disease despite stable treatment with anti-TNF α for at least 3 months at a stable dose or for at least one dose in case of lack of tolerance
Investigational drug	The drug whose properties are being tested in the study; this definition is consistent with US CFR 21 Section 312.3 and is synonymous with 'investigational new drug' or 'investigational medicinal product'
Investigational treatment	All investigational drug(s) whose properties are being tested in the study as well as their associated treatment controls. This definition is consistent with US CFR 21 Section 312.3 and is synonymous with "investigational new treatment." This includes any placebos, any active controls, as well as approved drugs used outside of their indication/approved dosage or tested in a fixed combination. Investigational treatment generally does not include other treatments administered as concomitant background therapy required or allowed by the protocol when used within approved indication/dosage
Medication number	A unique identifier on the label of each investigational / study drug package
Premature subject withdrawal	Point/time when the patient exits from the study prior to the planned completion of all study treatment administration and/or assessments; at this time all study treatment administration is discontinued and no further assessments are planned, unless the patient will be followed for progression and/or survival
Randomization number	A unique identifier assigned to each randomized subject, corresponding to a specific treatment arm assignment
Study drug/ treatment	Any treatment administered to the subject as part of the required study procedures; includes investigational treatment and any control drugs

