Taking into account the available safety data for the individual risks outlined in the IB, the expected risk profile of secukinumab from a mechanism of action perspective is anticipated to be similar compared with other approved cytokine-targeting therapies. In some trials, infections were numerically higher in the secukinumab treatment groups than in the placebo cohorts, although no dose-dependent increase in rates of serious infections was observed. This indicates that there may not be a direct exposure related effect on host defense. The safety data from the completed studies do not suggest any unexpected safety risk of concern or any particular pattern of event clustering other than those outlined in the IB. From the standpoint of the overall risk benefit assessment, the current trial with secukinumab is justified.

4 Population

The study population will be comprised of patients (≥ 18 years old at the time of consent) with moderate to severe AS who fulfill the modified New York criteria for ankylosing spondylitis (described in Appendix 3) with prior documented radiological evidence (x-ray or radiologist's report).

Patients must have a history of active AS and report active disease as measured by the following three assessments:

- total BASDAI ≥ 4 on a scale of 0-10
- spinal pain as measured by BASDAI question #2 ≥ 4 cm (0-10cm)
- total back pain as measured by visual analog scale (VAS) ≥ 40 mm (0-100 mm)

This is a global study and it is expected that approximately 450 subjects will be randomized. Approximately 80% of randomized patients will be from China (360 Chinese patients) in order to evaluate the efficacy and safety in this patient population. A screening failure rate of 30% and post-randomization drop-out rate of 10% at primary endpoint are anticipated. Enrollment will stop as soon as the target number of randomized subjects is reached. No more than 30% TNF-IR patients will be enrolled in the study.

Patients can be re-screened only once and no study-related re-screening procedure should be performed prior to written re-consent by the subject. Mis-randomization occurs when a subject who does not meet all eligibility criteria receives a randomization number in IRT in error; mis-randomized patients will be treated as screen failures and will not be re-screened.

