4.1 Inclusion criteria

Patients eligible for inclusion in this study have to fulfill **all** of the following criteria:

1. Patient must be able to understand and communicate with the investigator and comply with the requirements of the study and must give written, signed and dated informed consent before any study assessment is performed
2. Male or non-pregnant, non-lactating female patients at least 18 years of age
3. Diagnosis of moderate to severe AS with prior documented radiologic evidence (x-ray or radiologist's report) fulfilling the Modified New York criteria for AS ([Appendix 3](#)),
4. Active AS assessed by BASDAI ≥ 4 (0-10) **at Baseline**
5. Spinal pain as measured by BASDAI question #2 ≥ 4 cm (0-10 cm) **at Baseline**
6. Total back pain as measured by VAS ≥ 40 mm (0-100 mm) **at Baseline**
7. Patients should have had inadequate response or failure to respond to at least 2 NSAIDs at an approved dose for a minimum of 4 weeks in total and a minimum of 2 weeks for each NSAID prior to randomization, or less than 4 weeks if therapy had to be withdrawn due to intolerance, toxicity or contraindications
8. Patients who are regularly taking NSAIDs (including COX-1 or COX-2 inhibitors) as part of their AS therapy are required to be on a stable dose for at least 2 weeks before randomisation
9. Patients who have been on a TNF α inhibitor (not more than one) must have experienced an inadequate response to previous or current treatment given at an approved dose for at least 3 months prior to randomization or have been intolerant to at least one administration of an anti-TNF α agent
10. Patients who have previously been on a TNF α inhibitor will be allowed to entry into study after an appropriate wash-out period prior to randomization:
 - a. 4 weeks for Enbrel $^{\circledR}$ or "Yi Sai Pu" $^{\circledR}$ (etanercept) – with a terminal half-life of 102 \pm 30 hours (s.c. route)
 - b. 8 weeks for Remicade $^{\circledR}$ (infliximab) – with a terminal half-life of 8.0-9.5 days (s.c. route)
 - c. 10 weeks for Humira $^{\circledR}$ (adalimumab) – with a terminal half-life of 10-20 days (average 2 weeks) (s.c. route)
 - d. 10 weeks for Simponi $^{\circledR}$ (golimumab) – with a terminal half-life of 11-14 days
 - e. 10 weeks for Cimzia $^{\circledR}$ (certolizumab) – with a terminal half-life of 14 days

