4.2 Treatment groups

The summaries by treatment will primarily be performed by the randomized treatment but also by combination of randomized treatment and switch treatment. For some safety summaries (e.g. exposure-adjusted) the ‘switch’ treatment may be summarized separately.

- Randomized treatment:
 - AIN457 150 mg
 - Placebo
- Treatment sequence:
 - AIN457 150 mg
 - Placebo – AIN457 150 mg
- Switch treatments (for patients who cross-over):
 - AIN457 150 mg

5 Subgroup definitions

The primary and secondary endpoints will be analyzed by region (China and non-China). Analyses by previous use of TNF- α inhibitor will also be provided for total population and Chinese population.

6 Assessment windows, baseline and post baseline definitions, missing data handling

Baseline and post-baseline definitions

In general, a *baseline* value refers to the last measurement made prior to administration of the first dose of study treatment. A post-baseline value refers to a measurement taken after the first dose of study treatment.

Analysis visit windows

Analysis visit windows will be used for the data that is summarized by visit; they are based on the study evaluation schedule and comprise a set of days around the nominal visit day. For any assessment, there are protocol defined scheduled visits around which analysis visit windows were created to cover the complete range of days within the study. The analysis visit windows and rules for dealing with multiple measurements within the windows are described in [Appendix 16.1](#).

7 Subject disposition, background and demographic characteristics

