11.4 Analysis of primary variable

The primary efficacy variable is response to treatment according to the ASAS20 criteria at Week 16. The analysis of the primary variable will be based on the FAS patients.

Description

The ASAS Response Criteria (ASAS20) is defined as an improvement of $\geq 20\%$ and ≥ 1 unit on a scale of 10 in at least three of the four main domains and no worsening of $\geq 20\%$ and ≥ 1 unit on a scale of 10 in the remaining domain.

Statistical analyses

The statistical hypothesis for ASAS20 being tested is that there is no difference in the proportion of subjects fulfilling the ASAS20 criteria at Week 16 in secukinumab regimen versus placebo regimen.

Let p_0 denote the proportion of ASAS20 responders at Week 16 for Placebo regimen and p_1 denote the proportion of ASAS20 responders at Week 16 for Secukinumab 150 mg regimen,

In statistical terms, $H_0: p_1 = p_0$, $H_{A1}: p_1 \neq p_0$, i.e.

H_1 : Secukinumab 150 mg regimen is not different to placebo regimen with respect to ASAS20 response at Week 16

The primary analysis will be conducted via logistic regression with treatment, randomization stratum (region) as factors and baseline weight as a covariate. Odds ratios and 95% CI will be presented comparing secukinumab 150 mg regimen to placebo.

Supportive analyses

Sensitivity analyses and supportive analyses will be conducted in order to provide evidence that the results seen from the primary analysis are robust.

In order to determine the robustness of the logistic regression model used for the primary analysis, ASAS20 response at Week 16 will also be evaluated using a non-parametric

ANCOVA model ([Koch 1998](#)) with the same independent variables as the logistic regression model.

Interactions between treatment and selected baseline demographics and disease characteristics will be explored.

The impact of missing data on the analysis results of ASAS20 response will be assessed as well by repeating the logistic regression model using different ways to handle missing data. These may include, but are not limited to:

- Multiple imputation
- Observed data analysis

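### Previous TNF-alpha inhibitor use is capped, recorded and analysed as a subgroup, but it is neither a randomisation stratum nor a term in any primary or secondary model

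*Protocol*

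**What the plan says.** - **Randomisation.** Protocol 3.1: "The patients will be stratified at randomization according to the region (China and non-China"). No other stratum is named. The same section sets the regional mix: "Approximately 80% of randomized patients will be from China (360 Chinese patients").
- **Cap.** Protocol 3.1: "No more than 30% TNF α Inhibitor Incomplete Responders (TNF-IR) patients will be enrolled in the study". Section 4 (Population) repeats it: "No more than 30% TNF-IR patients will be enrolled in the study". Neither sets a limit by region.
- **Who is TNF-IR.** Under inclusion criterion 9, a patient with TNF-inhibitor exposure "must have experienced an inadequate response to previous or current treatment given at an approved dose for at least 3 months prior to randomization", or must have been intolerant. The glossary counts intolerance as inadequate response, and a second agent is excluded. In eligible patients, previous use (yes/no) and TNF-IR therefore coincide.
- **Models.** SAP 11.4: "The primary analysis will be conducted via logistic regression with treatment, randomization stratum (region) as factors and baseline weight as a covariate". The other binary endpoints use the same terms. The MMRMs in SAP 11.5 and 11.7 add visit, baseline value and their interactions. Protocol 9.4.2, 9.5.1 and 9.5.4 agree. None has a TNF term.
- **Subgroups.** SAP 5: "The primary and secondary endpoints will be analyzed by region (China and non-China"). It also plans analyses by previous TNF-inhibitor use, for the total and Chinese populations only.
- **Other uses.** Prior use is tabulated at baseline (Protocol 9.2, SAP 7.2). Protocol 9.4.4 allows further models with other baseline characteristics. SAP 11.4 commits to exploring treatment interactions with selected characteristics. Neither names TNF history.

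**The concern.** By capping the factor, tabulating it and planning a subgroup on it, the plan treats TNF history as relevant to response. The confirmatory estimates nevertheless take whatever split between arms chance gives, overall and within each region. The exposure is greatest in the roughly 90 non-China patients (60 v 30), where imbalance is largest and no TNF split is planned.

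A second question concerns the regional results. The cap applies to the trial as a whole, so the TNF-IR share may differ between China and non-China. A reader who sees different treatment effects in the two regions would then have no planned analysis that separates region from TNF history.

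**Working it through.** **Inputs from the documents:** 300 v 150; ASAS20 61.1% v 28.4%; partial remission 13.9% v 4.1%; 360 China and 90 non-China; cap 30%; two-sided 5%. **Assumed:** response is 10-20 points lower in TNF-IR patients (*g*), and the treatment effect differs between TNF-naive and TNF-IR patients by 5-20 points (*D*). The documents give neither.

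1. **The plan's power.** SE of the ASAS20 difference = √(0.611×0.389/300 + 0.284×0.716/150) = 4.63 points. The planned difference is 61.1 − 28.4 = 32.7 points. Power exceeds 99.9% by the normal formula and by exact Fisher enumeration, against about 99% stated. Partial remission gives 92.8% (normal) or 93.1% (Fisher), against 92% stated. The plan's figures reproduce.

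2. **Chance imbalance at the cap.** SD of the difference in TNF-IR share = √[p(1−p)(1/n₁+1/n₀)·N/(N−1)].
   - Overall, p = 0.30: √[0.21×(1/300+1/150)×450/449] = 4.6 points. P(difference ≥10 points) = 3.8%.
   - Non-China, 27 TNF-IR of 90: √[0.21×(1/60+1/30)×90/89] = 10.3 points. P(≥10) = 46%; P(≥15) = 22%.

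3. **Shift in the treatment difference given the imbalance.** 95% range = 1.96 × SD × *g*.
   - Overall: 1.96×4.6×0.10 = 0.9; at 0.20, 1.8 points. Set this against the SE of 4.63.
   - Non-China: 1.96×10.3×0.10 = 2.0; at 0.20, 4.0 points. The SE there is √(0.611×0.389/60 + 0.284×0.716/30) = 10.4 points.
   - The imbalance accounts for (0.046×*g*/0.0463)² of the variance overall: about 1% at *g* = 0.10 and 4% at 0.20.

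4. **Type I error.** In 4,000 simulated region-stratified trials per scenario (20-point TNF effect, no treatment effect, weight omitted), rejection was 4.8% without the term and 4.6% with it at equal 30% shares. With 12.5% TNF-IR in China and 100% outside it, the figures were 4.8% and 5.15%. Simulation error is √(0.05×0.95/4000) = 0.34 points, so none differs materially from 5%.

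5. **Power.**
   - Near the planning rates (TNF-IR 50% v 24%, naive 65.9% v 30.3%): about 100% either way.
   - Weaker effect (42% v 28.4%, *g* = 0.20): 80.8% without the term, 82.4% with it.
   - Partial remission (3,000 runs): 93.8% v 93.9% at a TNF-IR odds ratio of 0.5, and 93.2% v 94.1% at 0.2.
   - In the weaker-effect case the mean log odds ratio moved from 0.610 (SD 0.220) to 0.633 (SD 0.223). The gain comes from a better ratio of estimate to error (2.78 to 2.84), not from a smaller standard error.

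6. **Regional contrast.** Spurious difference in effect = *D* × (non-China share − China share).
   - The cap allows 0.30×450 = 135 TNF-IR patients. The limits are 90/90 outside China with 45/360 = 12.5% in China, or none outside with 135/360 = 37.5% in China.
   - Equal shares give 0. Shares of 25% in China and 50% outside (90 + 45 = 135) with *D* = 5-20 points give 1.2-5.0 points.
   - The SE of the contrast at planning rates is √[(0.611×0.389/240 + 0.284×0.716/120) + (0.611×0.389/60 + 0.284×0.716/30)] = 11.6 points.

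**The case against.** The strongest reply is that randomisation already deals with this. Chance imbalance is part of the sampling variance, type I error holds, and the overall shift is small beside a planned difference of 32.7 points. All of that stands. The model includes its only randomisation stratum, and choosing one more covariate is partly judgement.

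Some mitigation is already committed: the TNF subgroups, the baseline tables (also produced for the Chinese population under SAP 3) and the interaction work, which SAP 11.4 says will be done. Crude non-China counts could be obtained by subtraction. What is missing is narrower: any named TNF-adjusted estimate, and any planned TNF split outside China.

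Timing is a fair objection. SAP 11.5 describes a problem found during data cleaning before database lock, and the first lock follows the last Week 16 visit. Recruitment is therefore probably complete, and a late change to the confirmatory models also departs from the protocol text. Both points limit the fix.

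A reader might also infer that TNF history confounds the regional results. Treatment is randomised within each region, so lower response in TNF-IR patients affects both arms and cancels in expectation. An extreme split (100% v 12.5%) with *g* of 10-20 points would separate the regions by 0.875 × 10-20, or about 9-18 points. That is a gap in response level, not in treatment effect. The documents plan no formal test between regions.

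**Conclusion.** The point holds as a modest weakness in the analysis. An available prognostic candidate, which the plan itself singles out, is left out of both the randomisation and every primary and secondary model. At the cap, and with an assumed 10-20 point lower response in TNF-IR patients, the cost is a 95% conditional shift of about ±0.9 to ±1.8 points overall and ±2 to ±4 points outside China, plus 0-2 points of power. A lower TNF-IR share or a weaker TNF effect would shrink these figures.

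The regional contrast in treatment effect is affected only if shares differ by region and the effect differs by TNF status. The trial-wide cap permits the first; the documents are silent on the second.

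Three stronger readings are not supported:
- **That the primary test is at risk.** Simulated type I error stays near 5%, and power near the planning values is about 100% with or without the term.
- **That the cap counts consented rather than randomised patients**, because the glossary defines enrolment as "the point at which informed consent must be obtained". Protocol section 4 ends enrolment at the randomised target, in the same paragraph as the cap, so the randomised reading is the natural one.
- **That adding the term makes the regions comparable.** If every non-China patient were TNF-IR, the factor would be constant there and adjust nothing. A main effect also does not address effect modification.

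**What to change.** 1. **Models, before unblinding.** Add previous TNF-alpha inhibitor use (yes/no) as a factor beside region and baseline weight in the logistic models and MMRMs of SAP 11.4, 11.5 and 11.7, including the by-region and Chinese-population runs. Amend Protocol 9.4.2, 9.5.1 and 9.5.4 to match.
2. **Fallback rules.** Give the factor a place in the MMRM non-convergence order of SAP 16.2.1.2 and add it to the imputation model of SAP 16.2.3.1. The drop list in 16.2.3.1 names a variable, *status*, that is not in the template's variable list; define or correct it in the same edit.
3. **If the data are already unblinded,** keep the planned models and report the TNF-adjusted versions as a labelled sensitivity analysis.
4. **Display.** Tabulate TNF status by region and arm, and show regional results by TNF status, including non-China where numbers allow.
5. **Only if randomisation is still open,** make TNF-IR a second stratum.

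The cost is SAP and protocol wording and one degree of freedom per model. The adjusted odds ratio becomes conditional on TNF status as well, so it will differ slightly from the region-and-weight version. Rare endpoints may have sparse cells in the non-China run; the separation fallback in SAP 16.2.2.2 already covers that.
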